# 2.0 Rationale and Specific Aims

Our hypothesis is that precurarization with rocuronium, followed by a 2 minute interval prior to administering succinylcholine will prevent, or ameliorate, succinylcholine induced myalgias compared to not pretreating, or pretreating with a shorter time interval prior to succinylcholine administration.

Primary endpoint: Does the patient have myalgias post succinylcholine administration with pretreatment with Rocuronium 2 minutes prior?

Secondary endpoint?

\*Severity of myalgias

\*Onset of myalgias postop relative to succinylcholine administration

\*Correlation of myalgias with the presence of skeletal muscle fasciculation upon succinylcholine administration

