# 4.0 Enrollment/Randomization

All Endoscopic Retrograde Cholangiopancreatography (ERCP) procedures scheduled at IU Health University Hospital on adult patients (18+ years old) will be identified. Subjects will be contacted face-toface prior to surgery by one of the research team members. They will be informed about the study and all questions will be answered. The potential subjects will be given a copy of the informed consent form and authorization form. The subjects will then be contacted face-to-face in POCU on the day of surgery and if participation is agreed upon, written consent will be taken. All patients will receive general endotracheal anesthesia consistent with acceptable standards of care.

A total of 300 subjects will be randomized by a/ computer program into 3 groups (100 in each group):

- 1. Group 1 (Control): 0 mg/kg of rocuronium pretreatment and 1 mg/kg (rounded up to the nearest 10 mg) succinylcholine
- Group 2: 0.05 mg/kg (rounded up to the next mg) up to 5 mg of rocuronium pretreatment followed by 1.0 mg/kg (rounded up to the next 10mg) succinlycholine t = 1 min +/- 10 sec after pretreatment.
- 3. Group 3: 0.05 mg/kg (rounded up to the next mg) up to 5 mg of rocuronium pretreatment followed by 1.0 mg/kg (rounded up to the next 10 mg) succinlycholine t = 2 min +/- 10 sec after pretreatment.

Drug amount rounding takes into account the limitations to accurately measure drug doses in the clinical setting. Rocuronium is measured in a 1 ml tuberculin syringe with 1mg = 0.1ml. Rounding allows the provider to round to the next 0.1ml. Smaller increments cannot be accurately measured. Likewise, Succinylcholine is 20mg/ml and administered from a pre-labeled, calibrated 10 ml syringe. The above allowable rounding allows the provider to administer the drug to the next nearest 10mg=0.5ml for the same reason.

Randomization will be performed using Research Randomizer in blocks of 30. The primary investigator will inform the person doing the case as to what group the patients are randomized to. Both the patients and the research staff doing assessments will be blinded to the randomization.

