#### **5.0 Study Procedures**

After IRB approval from Indiana University Hospital and with written and verbal informed consent from each patient, 300 ASA I, II and III outpatients scheduled for elective Endoscopic Retrograde Cholangiopancreatography (ERCP) under general anesthesia will be enrolled in this randomizedcontrolled study. The patients and the study personnel performing post-op assessments will be blinded. Anesthesiologists cannot be blinded during this study since they will be required to draw up the study drugs as well as managing the wait time between rocuronium and succinylcholine. Patients are assigned to one of three groups (n = 100 each group). Each patient will undergo a standard IV induction of anesthesia (Lidocaine 1mg/kg, propofol 1-2 mg/kg titrated to effect, and succinvlcholine (administered as indicated by study group assignment). Study group details are as follows: Group 1 (Control) to receive no rocuronium and 1 mg/kg of succinylcholine (rounded up to the next 10mg). Groups 2 and 3 to receive 0.05 mg/kg (rounded up to the next 1mg) up to 5 mg of rocuronium; patients ranging from 50-120 kg. In Group 2, succinvlcholine administration will occur at 1.0 mg/kg (rounded up to the next 10 mg) at t = 1minute (+/-10 seconds) after pretreatment with rocuronium. In Group 3, succinylcholine 1mg/kg (rounded to the next 10 mg) will be administered at t = 2 minutes (+/- 10 seconds) after pretreatment. The Succinvlcholine-induced fasciculations will be noted on study assessment sheet as either present or absent. Myalgia assessment is to occur succinvlcholine administration at t = 3 hours and t = 24 hours and will be rated as described below.

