#### 6.0 Statistical Analysis

The statistical analysis will be conducted using SAS. Summary statistics will be calculated for the overall cohort, as well as by-treatment group. Categorical variables will be presented as frequencies and percentages, and groups will be compared with chi-square or Fisher's Exact tests. Distributions of the continuous variables will be assessed to determine if data transformations or non-parametric tests are needed. Continuous variables will be presented as mean and standard deviation and groups will be compared with ANOVA unless non-parametric tests are warranted, in which case, median and interquartile range will be calculated and Kruskal-Wallis tests will be used to compare groups. For variables with multiple measurements, these statistics will be given for each discrete time point. Myalgia will be assessed as both a categorical variable (any myalgia vs. none), and as an interval variable. A significance level of 5% will be used for all statistical comparisons.

To determine the effect of the treatments over time on the outcomes of interest, mixed models will be utilized, with fixed effects for treatment and time, as well as their interaction, and a random effect for subject. When necessary, additional variables may be added to adjust the models for other noted differences between the treatment groups.

Based on prior observation, the myalgia incident rate is 50%. With 100 patients in each of the three groups, will have 80% power to detect an odds ratio of 2.26 between any two groups, with two-sided tests and an alpha of 0.05 (5% significance level).

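### Fasciculations are scored at induction with no named observer and no definition, where the anesthesiologist knows the arm, so fasciculation results are open to arm-dependent misreading; the primary myalgia endpoint is not affected

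*Combined protocol and SAP*

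**What the plan says.** The whole description of the fasciculation measurement is in section 5.0 (Study Procedures): "fasciculations will be noted on study assessment sheet as either present or absent". No observer, threshold or observation window is given. Myalgia, by contrast, has a five-level scale with a description of each level.

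On who knows the arm, section 5.0 states "Anesthesiologists cannot be blinded during this study since they will be required to draw up the study drugs" and adds that they also manage the wait before succinylcholine. Section 4.0 (Enrollment/Randomization) says "The primary investigator will inform the person doing the case as to what group the patients are randomized to".

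On who is masked, the two sections differ in scope. Section 5.0: "The patients and the study personnel performing post-op assessments will be blinded". Section 4.0: "Both the patients and the research staff doing assessments will be blinded to the randomization". The second is not restricted to the post-operative period, but neither sentence mentions fasciculations or the induction room.

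Fasciculation enters the analysis in two ways. Section 2.0 lists as a secondary endpoint "Correlation of myalgias with the presence of skeletal muscle fasciculation upon succinylcholine administration". Section 6.0 has a general rule that would also cover a present/absent variable: "Categorical variables will be presented as frequencies and percentages, and groups will be compared with chi-square or Fisher's Exact tests".

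**The concern.** Fasciculation can be seen only at induction, just after succinylcholine. The one person the plan places there is told the group, draws up the drugs and times the wait. With no definition, faint or brief movement is left to judgement. The Background reports repeatedly that rocuronium reduces fasciculations, so an observer who knows the arm has a prior expectation. If borderline movement is read differently by arm, a between-group difference can be created, exaggerated or hidden. Arm information also leaks into the fasciculation variable. Because myalgia may itself differ by arm, that leak can produce an association between the two when all patients are pooled. Section 1.0 presents the fasciculation-myalgia relation as one of the questions the study hopes to address, and a call missed or misread at induction cannot be recovered later.

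**Working it through.** **Inputs from the documents.** 100 patients per group, two-sided alpha 0.05, myalgia rate 50%, detectable odds ratio 2.26 (all section 6.0). The documents give no fasciculation rate and no error rate, so everything below the first step rests on assumptions.

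**The plan's own figure.** An odds ratio of 2.26 from 50% corresponds to 1/(1 + 2.26) = 30.7%. With the two-sided pooled z-test, power = Φ[(d − 1.96·SE0)/SE1], where SE0 = √(2p̄(1−p̄)/n) and SE1 = √([p1(1−p1)+p2(1−p2)]/n). Here d = 0.193, p̄ = 0.403, SE0 = 0.0694, SE1 = 0.0680, and power is 80.0%. The stated 80% reproduces, but it concerns myalgia and does not bear on this point. The same test is used below.

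**(a) Creating a difference.** Assume the same true fasciculation rate p in control and in one pretreated group, and a fraction m of calls pushed toward expectation: absent called present in control, present called absent after rocuronium. Observed rates are p + (1−p)m and p(1−m), so the spurious difference is always m. Worked case, p = 0.50 and m = 0.10: 0.55 against 0.45, SE0 = 0.0707, SE1 = 0.0704, rejection probability 29%. Over true rates of 30% to 90%:

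| Error m | Rejection probability (nominal 5%) |
|---|---|
| 5% | 11% to 19% |
| 10% | 29% to 53% |
| 15% | 56% to 83% |

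**(b) How much depends on a common direction.** Take p = 0.60 and m = 0.15.
- All observers lean toward rocuronium: 0.60 + 0.40 × 0.15 = 0.66 against 0.60 × 0.85 = 0.51; rejection probability 57.7%.
- Only the pretreated group is misread: 0.60 against 0.51; about 25%.
- Half lean that way and half are neutral: 0.63 against 0.555; about 19%.
- Half lean each way: (0.66 + 0.51)/2 = 0.585 in both groups; no spurious difference, and the nominal 5% is kept.

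**(c) Hiding a difference.** Assume true fasciculation rates of 50% and 30.7% (the myalgia figures, borrowed for illustration) and errors in the opposite direction. Observed rates are 0.475 against 0.341 at m = 5%, 0.450 against 0.376 at 10%, and 0.425 against 0.411 at 15%. Power falls from 80% to 48.5%, 18.5% and 5.5%.

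**(d) The listed correlation endpoint.** Assume no link between fasciculation and myalgia within any arm, true fasciculation of 50% in all arms, myalgia of 50% in control and 30.7% in both pretreated groups, and errors as in (a). At m = 10%, observed fasciculation is 55% in 100 controls and 45% in 200 pretreated patients. The expected pooled table is:

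| | Myalgia | No myalgia |
|---|---|---|
| Fasciculation | 55.1 | 89.9 |
| No fasciculation | 56.2 | 98.8 |

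The pooled odds ratio is (55.1 × 98.8)/(89.9 × 56.2) = 1.08, against a true 1.00. At m = 15% it is 1.12 and at 20% it is 1.16. Within each arm it stays at 1.00, because the error here depends only on arm and true fasciculation status.

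**The case against.** **The scorer may be blinded.** Section 4.0 says without restriction that research staff doing assessments are blinded, and fasciculations go on the study assessment sheet. A reader might infer from section 5.0 that the anesthesiologist makes the call and that it is therefore unblinded. The documents do not say so; the observer is simply not named. This stands. But section 4.0 does not place a masked person at induction either, and someone watching the whole induction could see whether there was a pretreatment injection and a wait. The gap remains on either reading.

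**The expectation is not uniform.** A reader might take the Risks text in section 1.0 as evidence that staff will favour rocuronium. Those beliefs concern myalgia, and the group is described as divided. This stands: the text does not establish a direction of bias for fasciculations, and with mixed leanings the effect shrinks or cancels, as in (b).

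**No true difference is an unlikely starting point.** The Background cites studies in which rocuronium reduced fasciculations. This stands as a limit on (a): with a real reduction, misreading toward expectation would exaggerate it rather than create it. The estimate would still be biased.

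**The between-group comparison is not a listed endpoint.** Correct. It follows only from the general rule for categorical variables in section 6.0. The listed endpoint is the correlation, where the illustrated distortion is modest.

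**Conclusion.** The point holds as a weakness in a secondary measurement. As written, the plan leaves fasciculation to an unnamed observer applying no definition, in a room where the anesthesiologist knows the arm, and its two blinding statements do not agree in scope. Any between-group fasciculation comparison could be seriously biased: rejection probabilities of about 11% to 83% if 5% to 15% of calls err, all in one direction, with no true difference and true rates of 30% to 90%. For the fasciculation-myalgia correlation the illustrated distortion is modest: a pooled odds ratio of 1.08 to 1.16 at 10% to 20% error. These are conditional on assumed error rates. Neither size nor direction can be taken from the documents, and mixed leanings reduce or remove the effect.

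A reader might also infer that the trial's main result is compromised. It is not: myalgia is reported by blinded patients to blinded post-operative assessors. The change is worth making before enrolment, but the trial's main conclusion does not depend on it.

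**What to change.** 1. Reconcile the blinding statements in sections 4.0 and 5.0 so that they say whether the fasciculation scorer is masked, and name that role.
2. Define the call: any visible involuntary movement within a fixed window after succinylcholine, scored at once.
3. Have it scored by a room team member already present who is not told the group and who looks to the patient only when succinylcholine is announced.
4. Record on the assessment sheet who scored and whether they knew the arm.
5. In section 6.0, state that the fasciculation-myalgia association will be analysed within arm or adjusted for arm. This removes the part of the distortion that comes from arm alone; it does not repair misreading within an arm.
6. Where the scorer was unblinded, describe the fasciculation result as open-label.

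The cost is a definition line, two tick-boxes, a sentence in the analysis section and a short task for existing staff. Treatment, visits and sample size do not change. The downside is that masking in the room will be imperfect and some values will be flagged as unblinded.

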#### Myalgia assessment:

Subjects will by queried at the above time points about muscle pain and scored based on their answers as follows.

- 0 no pain / no muscle stiffness
- 1 mild muscle pain and/or stiffness at 1 or more sites that does not limit daily activity
- 2 Moderate muscle pain and/or stiffness at 1 or more sites that does not limit daily activity
- 3 Moderate generalized muscle pain and/or stiffness limiting daily activity

4 – Severe muscle pain and/or stiffness at 1 or more sites limiting movement and preventing daily activity

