Previous studies looking at the efficacy of pretreatment with rocuronium to prevent succinvlcholine fasciculations and / or myalgia were limited in many ways including, but not limited to, low numbers in the study groups, a lack of uniformity in the length of the case, and a lack of uniformity in the presence/absence or size of a surgical incision. Studies have demonstrated that patients with little surgical pain are more likely to complain of post-succinylcholine myalgias compared to patients who are preoccupied with terrible pain from surgical wounds. The length of the case also seems to impact the severity of post-surgical muscle pain independent of succinvlcholine use. The actual etiology of postsuccinvlcholine myalgia has not been fully elucidated. It was originally thought that the induction of fasciculations by the acetylcholine-like action of succinvlcholine at the neuromuscular junction caused muscle damage leading to myalgias, however, studies looking at the correlation between fasciculations and myalgias showed only a weak correlation. We hope to address some of these questions with this proposed study. Our group provides anesthesia to patients coming to Indiana University Hospital for ERCP (endoscopic retrograde pancreatography). ERCP cases are generally short (under 2 hours), are uniformly positioned, and do not result in a surgical wound. Because they are such short cases, yet still require general endotracheal anesthesia, succinvlcholine is the drug of choice in our group as it results in rapid intubating conditions with a very short duration of action. As this is a high volume center, we have a unique opportunity to study the effect of pretreatment with a nondepolarizing neuromuscular blocker

(rocuronium) on succinylcholine induced myalgias while enjoying a mitigation of the confounding variables mentioned above.

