# 3.0 Inclusion/Exclusion Criteria:

Inclusion Criteria:

- Undergoing elective Endoscopic Retrograde Cholangiopancreatography (ERCP) under general anesthesia
- Have been informed of the nature of the study and informed consent has been obtained
- ASA 1, 2 and 3

Exclusion Criteria:

- Patients will be excluded if they have chronic pain requiring daily opioid use greater than 30 mg PO morphine equivalent.
- Patients will also be excluded if their comorbid medical conditions require a true rapid sequence induction as precurarization with rocuronium increases the time to intubation which is undesirable in a patient who is at high risk for aspiration.
- Patients taking muscle relaxants at home for spasticity.
- Patients under the age of 18 years old.
- Any contraindication for using succinylcholine or rocuronium.
- Less than 50kg or greater than 120kg

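### No muscle-pain score is specified before succinylcholine, so prior pain that persists counts as myalgia; a baseline question is cheap, with a modest benefit of uncertain size

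*Combined protocol and SAP*

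**What the plan says.** Section 2.0 hypothesises that rocuronium given 2 minutes beforehand "will prevent, or ameliorate, succinylcholine induced myalgias". Its secondary endpoints include severity, "Onset of myalgias postop relative to succinylcholine administration" and "Correlation of myalgias with the presence of skeletal muscle fasciculation upon succinylcholine administration".

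Myalgia is scored 0 to 4 at 3 hours and 24 hours (Sections 5.0 and 10.0). The instruction is: "Subjects will by queried at the above time points about muscle pain and scored based on their answers as follows". Any mild muscle pain or stiffness scores at least 1, and nothing asks whether it was there before the drug. No earlier score is specified. Section 6.0 analyses the result as any myalgia versus none, and also as an interval variable.

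The pain-related exclusions in Section 3.0 are "chronic pain requiring daily opioid use greater than 30 mg PO morphine equivalent" and "Patients taking muscle relaxants at home for spasticity". Section 6.0 allows extra covariates in the models when needed, but names no baseline pain variable.

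**The concern.** The hypothesis concerns myalgia caused by succinylcholine, whereas the measure records whatever muscle pain or stiffness is present at follow-up. A patient with mild existing pain and low or no opioid use can enter, and if the pain lasts to 3 or 24 hours the patient is an event whatever the arm. Three things are at stake:

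- **Primary comparison.** Events that treatment cannot prevent dilute the difference between arms.
- **Onset and severity.** Without a time-zero score, pain at 3 hours cannot be divided into pain that began before the drug and pain that began after it. Randomisation does not help, because onset is a within-patient question.
- **Fasciculation correlation.** This is not a randomised contrast. Prior pain unrelated to fasciculation weakens it.

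The optional covariates in Section 6.0 cannot fill the gap, because a baseline score that was never collected cannot be added later.

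**Working it through.** **Inputs from the plan.** 100 patients per group (Section 4.0); control rate 50%, odds ratio (OR) 2.26, 80% power, two-sided alpha 0.05 (Section 6.0).

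**Plan's own figure.** An OR of 2.26 from 50% gives p2 = 1/(1 + 2.26) = 0.307. The pooled-variance formula for two proportions gives power 0.800, so the stated 80% reproduces. The simulated Pearson chi-square test without continuity correction gives 0.805.

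**Assumed input.** Let b be the share of patients whose prior pain persists to follow-up. The documents do not give it; 2, 5, 10 and 20% are used.

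**Reading 1: 50% and 30.7% are new-onset rates.** The observed rate is b + (1 − b)p. At b = 10%: 0.10 + 0.90 × 0.50 = 0.550 versus 0.10 + 0.90 × 0.307 = 0.376, an observed OR of 2.03. The table gives simulated power (400,000 trials per cell) for the planned chi-square test and for a Cochran-Mantel-Haenszel (CMH) test stratified by baseline pain, with the change in points in brackets. The baseline-positive share is b divided by the proportion persisting; patients whose pain does not persist respond like everyone else.

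| | b = 2% | 5% | 10% | 20% |
|---|---|---|---|---|
| Planned chi-square | 78.7 | 76.1 | 71.4 | 61.2 |
| CMH, all persist | 79.3 (+0.6) | 78.1 (+2.0) | 75.8 (+4.4) | 70.6 (+9.5) |
| CMH, 75% persist | 78.9 (+0.3) | 77.2 (+1.2) | 74.0 (+2.7) | 66.7 (+5.6) |
| CMH, 50% persist | 78.8 (about 0) | 76.3 (+0.3) | 72.3 (+1.0) | 63.1 (+1.8) |
| CMH, 25% persist | 78.3 (−0.3) | 75.7 (−0.4) | 70.7 (−0.7) | 59.8 (−1.4) |

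Bracketed changes can differ by a tenth or so from subtracting the first row, through rounding and simulation error. Under the null at b = 5% and 20%, the chi-square test rejects in 5.2 to 5.6% of trials and CMH in 5.0 to 5.1%, so neither is materially inflated. Part of each small negative change reflects this difference in size.

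**Reading 2: the 50% already includes prior pain.** The stated 80% power for an observed OR of 2.26 stands. The new-onset rates behind it are (0.50 − b)/(1 − b) and (0.307 − b)/(1 − b):

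| b | New-onset rates | New-onset OR |
|---|---|---|
| 2% | 0.490 vs 0.293 | 2.32 |
| 5% | 0.474 vs 0.270 | 2.43 |
| 10% | 0.444 vs 0.230 | 2.68 |
| 20% | 0.375 vs 0.133 | 3.90 |

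**A third combination.** If the 50% includes prior pain but the OR of 2.26 is meant for new-onset myalgia, formula power at b = 5, 10 and 20% is 73.6, 65.8 and 47.0%. Restricting to patients free of baseline pain, with all prior pain persisting, gives 76.9, 73.3 and 63.4%: about 3, 8 and 16 points more.

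**Interpretation under Reading 1, control arm, at b = 2, 5, 10 and 20%.**

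- Share of events with persisting prior pain, b/(b + (1 − b) × 0.5): 0.02/0.510 = 3.9%, 0.05/0.525 = 9.5%, 0.10/0.550 = 18.2%, 0.20/0.600 = 33.3%.
- If that pain is unrelated to fasciculation, the fasciculation–myalgia correlation is multiplied by (1 − b) × 0.5/√(r(1 − r)), with r = b + (1 − b) × 0.5: 0.980, 0.951, 0.905 and 0.816. That is a shrinkage of about 2, 5, 10 and 18%.

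**The case against.** Scoring only after treatment in a randomised comparison with blinded assessors is valid. The primary endpoint in Section 2.0 asks whether patients have myalgia after succinylcholine, which the planned measure answers; only the hypothesis speaks of induced myalgia. The size of the problem is wholly assumed, the exclusions already remove some painful patients, and at b = 2 to 5% the recoverable power is at most 0.6 to 2.0 points. The loss disappears under Reading 2. The recommended analysis keeps any myalgia as the event, so prior pain still counts. A baseline score also cannot remove other post-procedure muscle pain: Section 1.0 says case length seems to "impact the severity of post-surgical muscle pain independent of" succinylcholine use. Finally, Section 5.0 refers to an assessment sheet that is not part of the document.

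Most of this stands. It limits the point to an improvement, and differences of a few tenths of a point establish neither gain nor loss. Some table corners are also extreme: 20% persisting at 25% persistence implies that 80% of patients have baseline pain, so the 1.4-point loss overstates the likely cost. The unseen sheet means only that no baseline score is specified in the plan. The objection does not reach the onset and fasciculation endpoints, which need a time-zero score whatever b is found to be, or the fact that an uncollected score cannot be recovered.

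**Conclusion.** The concern holds, as a recommended improvement and not a flaw that invalidates the trial. There is no bias between arms, type I error is intact, and the planned test still answers whether there is any myalgia afterwards. What is lost is some sensitivity to induced myalgia and a clean reading of onset, severity and the fasciculation correlation.

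The size rests on b, on how often prior pain persists, and on what the 50% includes, none of which the documents give. Near b = 0 nothing is lost. Under Reading 1, up to b = 10%, stratifying recovers at most about 4.4 points; a gain near 10 points needs 20% of patients to have prior pain that all persists. The third combination gives larger gains. Confidence in the size is therefore only moderate; the omission itself is clear from the text.

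**What to change.** - **Collect it.** After consent and before induction, ask the same 0–4 question and record it in REDCap. The contact already exists: "The subjects will then be contacted face-to-face in POCU on the day of surgery".
- **Primary analysis.** Keep any myalgia as the event. Prespecify a CMH test stratified by baseline score 0 versus 1 or more, because Section 6.0 names only chi-square or Fisher tests for categorical variables.
- **Other analyses.** Add the baseline score to the mixed model, and also report onset and severity among patients with a baseline score of 0.
- **Sensitivity analysis only.** Report new-or-worse myalgia (score above baseline). It is not safe as the primary: the scale is global, so new pain at another site may not raise the score, and a patient starting at 4 cannot become an event. If no baseline-positive patient scores higher, it gains 0.4, 0.7, 1.6 and 4.3 points at b = 2, 5, 10 and 20% when all prior pain persists, but loses 1.3, 3.1, 5.8 and 12.9 points when half does.
- **Planning rate.** State in Section 6.0 whether the 50% includes pre-existing pain.

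The cost is one question and one field per patient, plus a short addition to Section 6.0. The reported odds ratio becomes baseline-adjusted, and the stratified test may be about 0.3 to 1.4 points weaker if only a quarter of baseline-positive patients have persisting pain.
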